- 2.2. Preliminary Data: We have developed a real-time TMS-EEG system which can continuously monitor the prefrontal theta rhythm (3-7 Hz) and trigger TMS pulses at specific phases with high accuracy. Our system has been validated in computational simulations and in proof-of-concept study in

MEDICAL PROTOCOL (HRP-590)

PROTOCOL TITLE: Investigating the causal and phase-dependent role of prefrontal theta oscillations in approach/avoidance behavior

VERSION DATE: 14/09/2024

healthy adults (Shirinpour et al., 2020). Recently, our real-time TMS-EEG system was used to investigate the phase-specific role of ongoing oscillations in motor cortex in adult participants, demonstrating robust performance and no unexpected side effects (Wischnewski et al., 2022).

- 2.3. Existing Literature: The combined application of TMS and EEG has established itself as a potent tool to probe and measure the causality of brain activity. It allows to accurately capture brain responses to the perturbation at specific times relative to the ongoing brain processes or cognitive tasks (Rogasch et al., 2016; Rogasch and Fitzgerald, 2013; Zrenner et al., 2016). Further, several recent studies have investigated the brain neurophysiology using real-time TMS-EEG for probing neural oscillations at different phases (Shirinpour et al., 2020; Schaworonkow et al., 2018; Zrenner et al., 2017). Our lab developed a novel closed-loop algorithm with higher accuracy compared to previous methods (Shirinpour et al., 2020). We recently applied the novel system to test the role of ongoing beta and mu oscillations in the motor cortex in healthy adults (Wischnewski et al., 2022). Moreover, the initial efforts to utilize real-time TMS-EEG for probing prefrontal activity and link between the prefrontal theta and cognition showed effectiveness and safety of such approach (Gordon et al., 2022).

3. Study Endpoints/Events/Outcomes

- 3.1. Primary Endpoint/Event/Outcome: The approach/avoidance test measures (reaction times to positive and negative emotional stimuli) during concurrent probing of ongoing prefrontal theta oscillations at peaks vs. troughs using TMS.
- 3.2. Secondary Endpoint(s)/Event(s)/Outcome(s): TMS-evoked potentials (TEPs) in concurrent EEG during the approach/avoidance test.

4. Study Intervention(s)/Investigational Agent(s)

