lay in the supine position within the scanner and be asked to relax. T1 and T2-weighted images will be collected to provide anatomical models for neural navigation during TMS. In addition, diffusion tensor imaging will be collected to assess structural connectivity of the prefrontal cortex, and BOLD fMRI contrast will be collected during the resting state to assess functional connectivity. All imaging modalities will follow standard Human Connectome Project (HCP) protocols (Harms et al., 2018), as routinely used in CMRR. Overall scanning time will be under one hour.

- 5.2.3. The approach/avoidance (Ap/Av) test: In the Ap/Av task, during each task trial, the volunteer sees on the screen a human face with either positive emotion (happiness, joy), negative emotion (anger, fear), or neutral emotion (Figure 1). During the congruent condition, the volunteer has to pull a joystick towards themself when they see a face with positive emotions and push away when they see negative emotions. In the incongruent condition, the responses with a joystick are the opposite. Neutral emotional stimuli require no response. When a joystick is pulled, the image become larger on the screen (imitating approach), when a joystick is pushed away – it become smaller (imitating avoidance). The reaction times to the stimuli and reaction time difference between the congruent and incongruent conditions constitute the primary test outcomes. We will perform four task blocks (approx. ten minutes each): two with congruent conditions and two with incongruent. The emotional stimuli are taken from publicly available, scientifically validated databases of emotional facial expressions, including Karolinska Directed Emotional Faces (KDEF; Lundqvist et al., 1998) and AffectNet (Mollahosseini et al., 2017). All stimuli can legally be used and redistributed for research purposes. The task presentation PC will be synchronized with the EEG amplifier and TMS machine using TCP/IP, UDP, and/or TTL protocols. Total time per session is 4 blocks of approx. 10 minutes, with approx. 5 minutes breaks in between.

MEDICAL PROTOCOL (HRP-590)

PROTOCOL TITLE: Investigating the causal and phase-dependent role of prefrontal theta oscillations in approach/avoidance behavior

VERSION DATE: 14/09/2024

[figure not shown]

Figure 1. Overview of a single experimental TMS-EEG session.

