- 15.1. Data Analysis Plan: We will analyze reaction times from the Ap/Av test using Hierarchical Bayesian Drift Diffusion Models (HDDM). This model is optimal for two alternative forced-choice cognitive tasks. It estimates single-trial performance in the presence of various sources of noise and trial-by-trial variations. The model will take reaction times as inputs and recover the variables of interest – speed of evidence accumulation (drift rate) and the decision thresholds for responding to the stimuli of positive and negative valence.

EEG from the stimulation and task periods will first be preprocessed. We will exclude noisy trials and interpolate noise channels, bandpass filter the signals (0.2-80 Hz) using Butterworth noncausal filters, suppress the line noise, and clean the data with extended InfoMax ICA. After preprocessing and artifact suppression, we will epoch the data around the TMS pulses, and calculate the TMS-evoked potentials in the left DLPFC caused by the stimulation at the peak and trough of theta oscillations.

- 15.2. Power Analysis: We estimated that medium effect size of Cohen's $d = 0.5$, which was observed in comparable studies (Shirinpour et al., 2020; Gordon et al., 2022), will be reached with a sample size of 26 volunteers.

- 15.3. Statistical Analysis: The HDDM parameters will be compared between the conditions using Generalized Linear Mixed-Effect Models (GLMM) with model outcomes as dependent variables, stimulation conditions (real vs control and peaks vs trough) as categorical independent variables, and participant IDs as a nuance variable. Further, post-hoc pairwise nonparametric tests will be applied between the conditions. Latency and magnitude of TMS-evoked potentials (TEPs) will be compared between the conditions using nonparametric cluster-based permutation test with false discovery rate correction for number of comparisons. Outcomes of TEPs and behavioral analysis will be correlated using Spearman statistics.

- 15.4. Data Integrity: Raw data and corresponding log files will be examined by the principal investigator on a regular basis during the data collection stage. The automatic log files will be generated automatically by the software which runs the EEG amplifier. The log files will be cross-checked

MEDICAL PROTOCOL (HRP-590)

PROTOCOL TITLE: Investigating the causal and phase-dependent role of prefrontal theta oscillations in approach/avoidance behavior

VERSION DATE: 14/09/2024

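### Section 15.3 tests outputs of a hierarchical model in a second-stage GLMM; if those outputs are shrunk toward condition-specific means or effects, which the plan does not exclude, type I error on the primary outcome is inflated

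*Combined protocol and SAP*

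**What the plan says.** The primary endpoint in Section 3.1 is "reaction times to positive and negative emotional stimuli", compared between stimulation at theta peaks and troughs. Section 15.1 fits an HDDM to the reaction times and recovers "speed of evidence accumulation (drift rate) and the decision thresholds for responding to the stimuli of positive and negative valence". Section 15.3 then states: "The HDDM parameters will be compared between the conditions using Generalized Linear Mixed-Effect Models (GLMM) with model outcomes as dependent variables". The factors are real versus control stimulation and peak versus trough, "and participant IDs as a nuance variable". The section continues: "Further, post-hoc pairwise nonparametric tests will be applied between the conditions".

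Three things are not stated: how conditions enter the hierarchy, whether point estimates or posterior draws are passed on, and at what level. The participant term suggests participant-level estimates, but Section 15.1 also says of the model: "It estimates single-trial performance in the presence of various sources of noise and trial-by-trial variations". No other comparison of conditions on the reaction-time outcome is planned.

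**The concern.** A hierarchical model pulls each participant's estimate toward a group value. Used as raw data in a second model, such estimates vary less between people than unpooled ones. If each condition has its own group value, the average difference between conditions is untouched while the person-to-person spread of that difference is compressed. The second-stage standard error is then too small. Shrinking participants' condition effects toward a group effect does the same, usually more strongly, because a within-person effect is estimated less reliably than a level.

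The GLMM and its post-hoc tests carry the whole primary comparison. As written, a reader cannot tell whether a p-value below 0.05 has its nominal meaning. The pooling structure could also be chosen after the data are seen.

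**Working it through.** The plan states no alpha, error rate or degree of shrinkage for this step, so it has no figure of its own to reproduce. The sample size of 26 (Sections 10.1 and 15.2) enters only as n.

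**Mechanism.** Let y be a participant's unpooled estimate in a cell, m the condition mean and w the reliability. The shrunken value is m + w(y − m). Its mean over participants is still m, but every deviation is multiplied by w. The paired t statistic is therefore the unpooled one divided by w, and under the null

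type I error = 2·P(t₂₅ > 2.06·w).

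This gives 6.2%, 7.6%, 9.2%, 11.2%, 16.2% and 31.3% at w = 0.95, 0.9, 0.85, 0.8, 0.7 and 0.5.

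**Responses per cell.** Section 5.2.5 gives 8 blocks of about 6 minutes and one trial every 2-6 s. At 4 s a block has 360/4 = 90 trials. Each site-by-phase cell takes two blocks (congruent and incongruent), so 180 trials. Section 5.2.3 says "Neutral emotional stimuli require no response"; I assume one third are neutral, leaving 120 responses, or 60 per valence. The full spacing range gives 40-120. Section 5.1 allows up to three sessions including MRI, and Section 5.3 speaks of three, so there may be one or two TMS-EEG sessions. Two double the counts: 120 at 4 s, 240 at most.

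**Shrinkage toward condition-specific means.** w = SD²/(SD² + se²), with se = 1.72/√N for drift. The 1.72 is the per-trial standard error from Fisher information at an assumed drift of 1.5 and threshold of 1.5, with non-decision time shared across cells. The between-person SD is assumed.

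| N per cell | se | SD 0.3 | SD 0.5 | SD 0.8 |
|---|---|---|---|---|
| 60 | 0.222 | 19.5% | 9.8% | 6.7% |
| 120 | 0.157 | 11.8% | 7.3% | 5.8% |
| 240 | 0.111 | 8.2% | 6.1% | 5.4% |

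Example: 0.25/(0.25 + 0.0493) = 0.835, and 2·P(t₂₅ > 1.72) = 9.8%. At an assumed drift of 2.0 (se = 2.01/√N), SD 0.5 gives 11.7% at 60 and 8.2% at 120, and SD 0.3 gives 25.0% at 60. For threshold, assumed SDs of 0.1 to 0.3 give 32% down to 7% at 60 and 18% down to 6% at 120.

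A null simulation of the drift table (normal approximation, 26 participants, four cells, w estimated from the data, 20,000 replicates) gave 20.1%, 9.8% and 6.6% at 60; 11.9%, 7.1% and 5.7% at 120; and 8.5%, 6.1% and 5.5% at 240. Unpooled estimates and one common prior mean gave 4.8-5.2% throughout.

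Full MCMC diffusion-model fits to null data (SD 0.5 for drift, 0.2 for threshold) gave 11.7% / 12.8% (drift / threshold) at 60 and 7.5% / 7.9% at 120. Wilcoxon tests on the same values gave 10.2% / 11.3% and 6.0% / 7.6%. One common mean gave 4.9% / 5.3% and no pooling 5.1% / 6.2%. Convergence of these fits was not documented, so I use them only as support for the closed form.

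**Shrinkage of condition effects.** A site or phase contrast is the mean of two cells minus the mean of two others. With person-by-cell SD s, its true variance between people is s² and its error variance is se², so w = s²/(s² + se²).

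| N per cell | s = 0.1 | s = 0.2 | s = 0.4 |
|---|---|---|---|
| 60 | 73% | 37% | 13% |
| 120 | 56% | 21% | 9% |

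Full fits at s = 0.2 (drift) and 0.08 (threshold), 60 responses, gave 37% / 41%.

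**Posterior draws entered as rows.** Twenty draws per cell in a random-intercept model gave 59-74%.

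**The case against.** The strongest reply is that Section 15.3 is incomplete and not demonstrably wrong. Nothing in it points to condition-specific means or shrunken effects, and the same words fit a common prior mean or unpooled estimates, where the test holds its level. This stands: a reader might infer that the planned tests are bound to reject too often, and the documents do not support that.

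A reader might also infer that the fault lies in failing to carry first-stage uncertainty forward. That is not so. Unpooled estimates carry nothing forward either, yet hold about 5%, because their noise appears in the second-stage residual. The cause is the shrinkage.

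The size is also open to challenge. All SDs are assumed. With two TMS-EEG sessions the central inflation under condition-specific shrinkage is only 7-8%, and the 6.0% Wilcoxon rate for drift (Monte Carlo standard error 1.2-1.4 points) cannot be told apart from 5%. Other features push the other way. Section 5.2.3 makes the congruent-incongruent difference a primary test outcome; splitting by congruency halves 60 to 30 responses, where w = 0.25/(0.25 + 0.0986) = 0.72 and the error is about 15%. Section 5.2.3 also gives four blocks of about ten minutes against eight of about six elsewhere, and those passages must be reconciled.

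Finally, a one-stage model is not automatically sound: a tight half-normal prior on the contrast SD gave 11.4% in a normal-approximation check. That stands, and it is why the fix asks for stated priors and a simulation check.

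**Conclusion.** The concern holds in conditional form. The plan does not exclude two pooling structures under which its only comparison of conditions on the primary outcome rejects too often. Under condition-specific shrinkage the error is roughly 6% to 20% for drift SDs of 0.3 to 0.8 and 60 to 240 responses per cell; it approaches nominal where reliability is high and reaches 25% at drift 2.0 in the least reliable case. Under shrunken condition effects it runs from about 9% to over 70% at 60 to 120 responses, and no single value in that range should be quoted as the expected rate. Post-hoc rank tests on the same values do not remove the problem.

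These ranges rest on assumed between-person and person-by-cell SDs, diffusion parameters and the share of neutral trials. They show what is plausible and do not predict this trial's error rate. The point should be fixed before analysis; confidence in its size is medium.

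**What to change.** In Section 15.3, replace the second-stage GLMM and post-hoc tests on HDDM outputs. Enter site, phase and their interaction as within-participant regressors on drift rate and threshold inside the hierarchical model, with participant-level random effects on those contrasts. Base inference on the group-level posterior. State the priors in advance, with priors on the contrast SDs that are not tight, and state a decision rule whose error rate is checked by simulation at n = 26. In the full fits a 95% credible interval excluding zero, with flat priors on the SDs, rejected in 5.3% (drift) and 6.1% (threshold) of null tests, with a Monte Carlo standard error of about 1 point. The random effects matter: intervals from condition-specific group means that ignored within-person pairing rejected in 0.1%.

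If a GLMM is kept, run it on trial-level reaction times, with participant random slopes for the contrasts, or on non-hierarchical estimates per participant and condition, which have correct size but are noisier. Do not enter shrunken estimates or stacked posterior draws as data. If draws are used, combine them by multiple-imputation rules, which gave about 1-4.5% in a normal-approximation check.

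The cost is SAP wording, extra model-fitting time and one simulation check. No new data are needed.

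### The section 15.3 mixed model omits valence and congruency, so a one-valence phase effect is either diluted by pooling or judged by separate tests whose difference is never tested

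*Combined protocol and SAP*

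**What the plan says.** Section 3.1 gives the primary endpoint as "reaction times to positive and negative emotional stimuli", compared between stimulation at theta peaks and troughs. Section 15.1 says the drift diffusion model will recover drift rate and "the decision thresholds for responding to the stimuli of positive and negative valence". Valence clearly applies to the thresholds; whether it also applies to drift rate is ambiguous.

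Section 5.2.3 makes the joystick response depend on valence and task rule together. In the congruent rule, positive faces are pulled and negative faces pushed; in the incongruent rule this is reversed. The same section names the congruent-minus-incongruent reaction-time difference among the primary test outcomes.

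Section 15.3 gives the behavioural test: the "HDDM parameters will be compared between the conditions using Generalized Linear Mixed-Effect Models (GLMM) with model outcomes as dependent variables". The explanatory terms are "stimulation conditions (real vs control and peaks vs trough) as categorical independent variables", with "participant IDs as a nuance variable". It adds that "post-hoc pairwise nonparametric tests will be applied between the conditions". No section names a valence term, a congruency term or an interaction.

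**The concern.** The outcome is built on valence, but the model that tests it is not. Two analyses fit the text.

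- **Pooled.** Positive and negative parameters enter one model with no valence term. An effect present in one valence is diluted, and effects of opposite sign offset each other.
- **Separate.** Each valence has its own model. Nothing then tests whether the phase effect differs between them. Significance in one and not the other could be reported as valence-specific, although two equal effects often produce that pattern by chance.

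The post-hoc tests do not close the gap: a pairwise peak-versus-trough comparison is not a test of whether that difference varies with valence. The choice between the two analyses is also left open until the data have been seen.

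**Working it through.** **Inputs.** From section 15.2: n = 26 and d = 0.5. From section 5.1: a within-participant crossover, hence paired contrasts. Not in the documents, so assumed: 5% level, one- or two-sided; the peak-minus-trough contrast has SD 1 in each valence; the two contrasts correlate at ρ = 0 to 0.7. Paired t-tests stand in for the planned mixed model.

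**1. The plan's own figure.** Power comes from the noncentral t with 25 df and noncentrality d√n = 0.5 × √26 = 2.55.

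- One-sided: power 79.8%. The n for 80% is 27 (25 by normal approximation), so 26 is reproduced.
- Two-sided: power 68.8%. The n for 80% is 34 (32 by normal approximation), so 26 is not reproduced.

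Section 15.2 states neither sidedness nor the contrast to which d = 0.5 belongs, so both versions are carried where they matter.

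**2. Pooled, effect of 0.5 in one valence only.** The average has mean 0.5/2 = 0.25 and SD √((1+ρ)/2). At ρ = 0 the standardised effect is 0.25/0.707 = 0.354. If the effects are +0.5 and −0.5 the mean is zero, and the test rejects in 5% of trials.

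**3. Separate, true effect 0.5 in both valences.** At ρ = 0, the chance that exactly one test is significant is 2 × 0.688 × 0.312 = 0.43 two-sided, or 2 × 0.798 × 0.202 = 0.32 one-sided. Other correlations were simulated. A direct test of the difference rejects in 5% of trials at every ρ.

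**4. The missing test, effect of 0.5 in one valence only.**

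- Phase-by-valence at DLPFC alone: standardised effect 0.5/√(2(1−ρ)).
- Relative to vertex, assuming no effect there and equal, independent vertex variance: 0.5/√(4(1−ρ)). At ρ = 0 this is 0.25.

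| ρ | Power, pooled (two-sided) | Exactly one significant, two-sided | Exactly one significant, one-sided | Power, phase × valence, DLPFC only (two-sided) | Power, phase × valence, relative to vertex (two-sided) |
|---|---|---|---|---|---|
| 0 | 41% | 43% | 32% | 41% | 23% |
| 0.3 | 33% | 36% | 27% | 54% | 31% |
| 0.5 | 29% | 30% | 23% | 69% | 41% |
| 0.6 | 28% | 27% | 21% | 78% | 49% |
| 0.7 | 26% | 23% | 18% | 89% | 61% |

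The comparator for the pooled column is 69%, the two-sided power when the affected valence is tested alone. At a smaller common effect of d = 0.3, the two-sided rate of exactly one significant result is almost the same (43% at ρ = 0, 23% at ρ = 0.7).

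**5. Why congruency must enter too.** Code valence V = +1 (positive) or −1 (negative), and rule C = +1 (congruent) or −1 (incongruent). By section 5.2.3, pull versus push is the product V × C. Within one rule C is constant, so valence and movement direction coincide up to sign and no test can separate them. With both rules in the model, phase × V concerns emotion, phase × V × C concerns movement direction, and phase × C concerns the congruent-minus-incongruent difference.

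**The case against.** The strongest reply is that the plan never proposes a valence-specific hypothesis. Section 1.1 asks about theta phase and approach/avoidance behaviour, and no rule says that significance in one valence alone will be read as specific to it. This stands, and it limits the point. A reader might infer that the study would publish a false valence-specific finding up to 43% of the time. The documents do not support that: the percentages are how often the misleading pattern appears, and it becomes an error only if it is interpreted that way.

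A reader might also infer that the phase comparison itself is invalid, or that valence effects must vanish. Neither follows. A main effect of phase remains testable, and complete cancellation needs equal and opposite effects; otherwise there is dilution. Nor can one say which analysis is planned, since section 15.3 is silent.

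It is also fair to say that approach/avoidance is movement direction rather than valence, so adding valence alone would be an incomplete repair. This stands and shapes the fix. Finally, the figures rest on an assumed correlation, equal SDs and t-tests in place of mixed models on diffusion parameters. They also depend on sidedness: on the one-sided basis that reproduces n = 26, the rates fall to 32–18%. They show the scale of the problem and do not predict this study's results.

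**Conclusion.** The gap is real, and section 15.3 should be revised. The outcome and estimated parameters refer to valence, and the task defines approach and avoidance through valence and congruency, but the model contains neither factor and no interaction.

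Under the stated assumptions, pooling leaves about 41–26% power for a one-valence effect that would have 69% if tested alone. Separate testing of equal effects gives a one-valence-only pattern in about 43–23% of trials two-sided, or 32–18% one-sided. The consequence is confined to valence-specific or approach/avoidance-specific claims and to the power of a pooled analysis.

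**What to change.** Rewrite section 15.3 as follows.

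- Fit one model per diffusion parameter with site × phase × valence × congruency and by-participant random effects. If each participant contributes one estimate per cell, the highest-order participant slope cannot be separated from the residual; state which slopes are kept.
- Use the phase contrast at DLPFC relative to vertex, averaged over valence and congruency, as the overall test.
- Allow a valence-specific claim only from the phase-by-valence contrast (DLPFC relative to vertex), and an approach/avoidance-specific claim only from a contrast that also involves congruency. Say in advance whether that means movement direction or the congruent-minus-incongruent difference.
- Report single-valence estimates with intervals, as descriptive.
- State in section 15.1 whether drift rate is also estimated by valence.

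The cost is analysis wording and model fitting. Section 5.1 already crosses four task-and-phase types with verum and sham (4 × 2 = 8 blocks), and section 5.2.3 presents positive and negative faces under both rules.

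The downside should be stated openly. At n = 26 the valence contrast relative to vertex has about 23–49% power for d = 0.5 in one valence (ρ = 0 to 0.6), and n = 26 was not shown to be sized for it. A null result on that contrast would be inconclusive and should not be reported as evidence that the phase effect is the same for both valences.

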volunteers will be blinded to the conditions. During each session, volunteers will first perform a task training and a short (approx. 5 min) block of the approach/avoidance task (Ap/Av) without TMS to record intrinsic EEG activity and use it for calibrating the real-time TMS-EEG system (Shrinpour et al., 2020). Then, volunteers will perform 8 main blocks of approach/avoidance tasks with TMS (approx. 6 minutes per block) in randomized order: 1. congruent task + TMS at theta peaks, 2. congruent task + TMS at theta troughs, 3. incongruent task + TMS at theta peaks, and 4. incongruent task + TMS at theta troughs. During each task trial, the volunteer will receive a single burst of TMS (up to three pulses) at the peak or trough of ongoing theta rhythm. In the verum TMS-EEG condition/block, we will apply TMS pulses over the left DLPFC based on the left DLPFC theta oscillations. In the sham condition/block, TMS will be applied over the head vertex (which should not induce changes in the prefrontal activity but will induce the same sensory effects). EEG will be recorded throughout the TMS-EEG sessions. In addition, electrooculography and heart rate will be recorded together with EEG using non-invasive sensors for the accurate removal of ocular and cardiac artifacts. There will be 3-5 min breaks in-between the blocks for rest. The total number of TMS pulses per day will not exceed 3,000 pulses, many times lower than the established safety limit of 90,000 pulses per day (Cole et al., 2022, 2020).

[figure not shown]

Diagram 1: Experimental pipeline with timing.

5.2. Study Procedures:

5.2.1. Initial questionnaires: during the initial visit, each volunteer will fill out standardized self-reported questionnaires regarding their demographic data and emotional assessment. These include the Patient Health Questionnaire (PHQ-9), General Anxiety Disorder (GAD-7) tool, and Quick Inventory of Depressive Symptomatology – Self-Rated (QIDS-SR-16). Total time necessary to complete all questionnaires is approx. 25 minutes.

5.2.2. MRI: During the first session, 3T MRI scans will be performed at the Center for Magnetic Resonance Research (CMRR). Participants will

MEDICAL PROTOCOL (HRP-590)

PROTOCOL TITLE: Investigating the causal and phase-dependent role of prefrontal theta oscillations in approach/avoidance behavior

VERSION DATE: 14/09/2024

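### The analysis section has no term for task congruency, so the congruent–incongruent difference listed among the primary test outcomes, and its change with theta phase, have no specified test

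*Combined protocol and SAP*

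**What the plan says.** **Design.** Section 5.1 pairs each task version with each phase; the list of block types includes "2. congruent task + TMS at theta troughs, 3. incongruent task + TMS at theta peaks". Verum and sham blocks form a further factor. Section 5.2.3 explains the task versions: pull for positive and push for negative faces when congruent, and "In the incongruent condition, the responses with a joystick are the opposite".

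**Outcomes.** Section 3.1 gives the primary endpoint as test measures, specified in parentheses as "reaction times to positive and negative emotional stimuli", with TMS at peaks versus troughs. It does not mention congruency. Section 5.2.3 says: "The reaction times to the stimuli and reaction time difference between the congruent and incongruent conditions constitute the primary test outcomes".

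**Analysis.** Section 15.1 passes reaction times to the HDDM: "The model will take reaction times as inputs and recover the variables of interest", namely drift rate and "the decision thresholds for responding to the stimuli of positive and negative valence". Valence is named there and congruency is not. Section 15.3 compares the HDDM parameters in a mixed model "with model outcomes as dependent variables" and "stimulation conditions (real vs control and peaks vs trough) as categorical independent variables, and participant IDs as a nuance variable". It states no interaction. Post-hoc pairwise nonparametric tests across conditions follow.

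**The concern.** A two-level factor built into every block, and a difference score that 5.2.3 ranks with the primary outcomes of the test, are both absent from the analysis. Reaction times appear only as HDDM input, so the reaction time difference is not a dependent variable, and no term asks whether phase changes the congruency effect.

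This bears on the objective in section 1, a causal effect of theta phase on approach/avoidance behaviour. The same face calls for opposite movements in the two tasks. A phase effect common to both tasks and one that differs between them are therefore different findings. With the handling of congruency left open, it could be settled after the data are seen, and a null phase result could reflect that choice rather than the data.

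**Working it through.** **1. Factors in the design against factors in the analysis**

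| Factor | Design (5.1, 5.2.3) | HDDM (15.1) | Mixed model (15.3) |
|---|---|---|---|
| Verum/sham | yes | not stated | yes |
| Peak/trough | yes | not stated | yes |
| Congruency | yes | no | no |
| Valence | yes | yes | no |

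The peak–trough comparison in 3.1 is in the model. The congruency difference and phase × congruency are not.

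**2. The plan's own figure.** Section 15.2 gives N = 26 for d = 0.5 without alpha, sidedness, power or the contrast meant. A paired t-test with N = 26 has 79.8% power one-sided at 5% and 68.8% two-sided at 5%. The figure therefore comes close to 80% power only under the one-sided assumption. It cannot show which contrast was sized.

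**3. Averaging over congruency.** Let phase shift a parameter by a in the congruent task and b in the incongruent task. The average effect is (a + b)/2. With a = b = x it is x; with an effect in one task only it is x/2; with a = −b it is 0. This is algebra and needs no variance assumption.

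**4. Estimating by congruency but omitting it from the model.** The assumptions, none from the documents, are:
- 16 cells per participant (site × phase × congruency × valence), n = 26, so 416 values
- random intercept only, independent residuals with SD 1, two-sided 5%
- a shift of x = 0.5 in the verum-peak cells, the same in both tasks
- test term site × phase, which 15.3 does not state

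The contrast is a difference of differences of four means of four cells each. Its variance per participant is 4 × (1/4) = 1, so its standardised mean is 0.5 × √26 = 2.55. Residual df are 416 − 26 − 3 = 387, with critical t 1.966. A congruency difference of m SD that is not modelled adds 416 × (m²/4)/387 = 0.269m² to the residual variance. The effective critical value is 1.966 × √(1 + 0.269m²), and power is approximately Φ(2.55 − that value).

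| m | Residual SD | Critical value | Power | Type I error |
|---|---|---|---|---|
| 0 | 1.000 | 1.966 | 72% | 4.9% |
| 1 | 1.126 | 2.215 | 63% | 2.7% |
| 2 | 1.440 | 2.832 | 39% | 0.5% |

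Simulation with 20,000 replicates agrees: 72.1, 63.2 and 39.1% power, and 4.9, 2.6 and 0.5% type I error.

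**5. Modelling congruency.** In the same simulation, site × phase power returns to about 72% at every m. Site × phase × congruency has about 72% power when the shifts are equal and opposite, and about 24–25% when only one task is affected.

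**6. Trials per cell.** By the timing in 5.2.5, a block of about 6 minutes is 360 s. At one trial per 4 s that is 90 trials. Assuming one third are neutral, 60 need a response, or 30 per valence. At 6 s and 2 s the figures are 20 and 60. This assumes eight blocks, one per site × phase × congruency cell, in one TMS-EEG session. Two sessions double it to about 60 (40–120).

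**7. Sharing alpha.** For a paired contrast with n = 26 and d = 0.5, two-sided power is 68.8% at 5% and 57.1% at 2.5%.

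**The case against.** **Sections 3.1 and 5.2.3 do not contradict each other.** A reader might infer a conflict over what is primary. Section 3.1 omits congruency but does not call the difference non-primary, and the wording in 5.2.3 can mean the main readouts of the task. This stands: the defect is an ambiguity by omission.

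**The endpoint in 3.1 is analysed.** Also correct. Reaction times go through the HDDM and peak versus trough is in the model. It would be wrong to infer that the primary endpoint has no test.

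**The post-hoc tests may cover congruency.** Section 5.2.3 does call the two task versions conditions. But the only conditions 15.3 spells out are the stimulation conditions, and its tests act on HDDM parameters, not on the reaction time difference. Even if congruency were included, pairwise tests would not specify whether phase changes the congruency effect.

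**A difference score might be the intended dependent variable.** It would cancel a phase effect common to both tasks. The text gives little support: 15.3 uses HDDM parameters, and the only difference score described is in reaction times.

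**The power figures are fragile.** Largely correct.
- Site × phase is not stated in 15.3, and 3.1 does not mention sham.
- If only one task is affected, power with congruency omitted at m = 1 is about 15.6% or 18.6%, depending on which task has the higher mean.
- There are no random slopes. A slope SD of 0.5 lowers the paired contrast to d = 0.5/√1.25 = 0.447 and 59.2% power. A slope SD of 1 gives d = 0.5/√2 = 0.354 and 41.1% power, and the random-intercept test's type I error then rises to about 10%.
- Shrinkage in a hierarchical fit would break the independence of residuals.

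The textual gap does not depend on any of these figures.

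**Conclusion.** The point holds and should be fixed before analysis. Followed as written, the plan leaves the congruency difference, and any change in it with phase, without a model term or a secure test. Section 3.1 does not settle whether that difference is an endpoint or a readout.

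The cancellation from averaging is exact for effects of opposite sign and partial for others. The documents predict no signs, so they do not support inferring that phase effects will be lost. The fall from 72% to 63% or 39% illustrates how an omitted main effect makes the phase tests conservative. It assumes the stated variances, a random intercept only and a site × phase term. It is not a forecast for this study.

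**What to change.** - **Section 15.1:** estimate drift rate and decision threshold by congruency.
- **Section 15.3:** add congruency as a fixed factor and state its interactions. To test whether phase changes the congruency effect, use phase × congruency within verum, or site × phase × congruency if the sham-controlled contrast is intended. Say which.
- **Sections 3.1 and 5.2.3:** state in both whether that contrast is primary or secondary. If the reaction time difference is only a task readout, say so.

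Adding valence terms to the mixed model is a separate choice and is not needed to close this gap.

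**Cost.** A few model terms and revised wording; no new data. Cell-level HDDM estimates become noisier, resting on about 30 response trials per congruency-by-valence cell with one TMS-EEG session or about 60 with two, if one third of trials are neutral. Sections 5.1 and 5.3 leave the number of TMS-EEG sessions open. If the phase contrast and the congruency contrast are both primary, sharing alpha lowers power at d = 0.5 from 69% to 57%. Making one of them secondary avoids that loss.
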